The overall safety and tolerability profile of brolocizumab was consistent with aflibercept, an established therapy in patients with nAMD. While there was a higher incidence of intraocular inflammation (IOI) AEs for brolocizumab compared to aflibercept, no preferred term (PT) was reported for more than 1.5% of patients. Over 90% of IOI AEs were mild to moderate in severity and 79% resolved with no sequelae. The impact of IOI on the benefit-risk balance of brolocizumab is considered to be low.

Adverse events (AEs) of Intraocular inflammation, including retinal vasculitis and/or retinal vascular occlusion have occurred since the Oct-2019 marketing authorization approval for brolocizumab (Beovu®) in the treatment of nAMD. These AEs may result in severe vision loss. Results of the mechanistic study BASICHR0049 of blood samples from nAMD patients exposed to brolocizumab and having subsequently developed Retinal Vasculitis (RV) and/or Retinal Vascular Occlusion (RO) taken together with accumulated data of the association of treatment-emergent immunogenicity and intraocular inflammation (IOI) indicate a causal link between the treatment-emergent immune reaction against brolocizumab and the brolocizumab-related "Intraocular inflammation, including retinal vasculitis and/or retinal vascular occlusion". This finding supports the requirement to discontinue treatment with brolocizumab in patients who develop events of Intraocular inflammation, including RV and/or RO.

Based on clinical studies, IOI related adverse events, including retinal vasculitis and retinal vascular occlusion, were reported more frequently in female patients treated with brolocizumab than male patients (e.g. 5.3% females vs. 3.2% males in HAWK and HARRIER, Novartis data on file).

In addition, based on USM (CRTH258AUS04 FIR), the brolocizumab dosing interval should not be less than 8 weeks beyond the loading period, that is not allowed in the present study protocol.

Intravitreal injections, including those with brolocizumab, have been associated with endophthalmitis and retinal detachment. The injection procedure must be carried out under aseptic conditions. Patients should be instructed to report any symptoms suggestive of the above-mentioned events without delay.

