## 9 Study discontinuation and completion

### 9.1 Discontinuation

#### 9.1.1 Discontinuation of study treatment

Discontinuation of study treatment for a patient occurs when study treatment is stopped earlier than the protocol planned duration, and can be initiated by either the patient or the investigator.

The investigator must discontinue study treatment for a given patient if he/she believes that continuation would negatively impact the patient's well-being.

The investigator and/or referring physician will recommend the appropriate follow-up medical care, if needed, for all patients who are prematurely withdrawn from the study.

Study treatment must be discontinued under the following circumstances:

- Patient requires treatment on a q4w interval after the initiation phase, i.e., after the three monthly injections at Baseline, Week 4, and Week 8, followed by the first interval extension
- Patient develops intraocular inflammation, including retinal vasculitis and/or retinal vascular occlusion
- Patient/guardian decision
- Pregnancy
- Use of prohibited treatment
- Any situation in which study participation might result in a safety risk to the patient

If premature discontinuation of study treatment occurs, the following should be done as appropriate:

- The investigator should make a reasonable effort to understand and document the primary reason for the patient's premature discontinuation of study treatment using the appropriate eCRF page.
- Patients who prematurely discontinue study treatment for any reason should return 4 weeks after last study treatment to perform the assessments for early treatment discontinuation (ETD). Please refer to [Table 8-1](#), except for patients who withdraw their consent from the study and do not wish to do so (refer to [Section 9.1.2](#)).
- After these assessments are performed, patient can be switched to standard of care (SOC) anti-VEGF IVT as per investigators discretion. IVT injection is contraindicated in patients with active intraocular or periocular infections and in patients with active intraocular inflammation; therefore, the investigators must verify that these conditions are not present in the study eye prior to every injection.
- After premature study treatment discontinuation, at a minimum till week 48, in abbreviated visits, the following data should be collected at clinic visits or via telephone/email contact:
  - New/concomitant treatments

- Adverse events/Serious Adverse Events
- BCVA

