## 10.1 Definition of adverse events and reporting requirements

### 10.1.1 Adverse events

An AE is any untoward medical occurrence (e.g. any unfavorable and unintended sign, symptom or disease) in a patient after providing written informed consent for participation in the study. Therefore, an AE may or may not be temporally or causally associated with the use of a medicinal (investigational) product.

The investigator has the responsibility for managing the safety of individual patient and identifying AEs.

Novartis qualified medical personnel will be readily available to advise on trial related medical questions or problems.

The occurrence of AEs must be sought by non-directive questioning of the patient at each visit during the study. AEs may also be detected when they are volunteered by the patient during or between visits or through physical examination findings, or other assessments.

AEs must be recorded in the Adverse Events eCRF under the signs, symptoms or diagnosis associated with them, accompanied by the following information (as far as possible) (if the event is serious refer to [Section 10.1.2](#)):

1. The severity grade (mild, moderate or severe as defined below)
  - mild: usually transient in nature and generally not interfering with normal activities
  - moderate: sufficiently discomforting to interfere with normal activities
  - severe: prevents normal activities
2. Its relationship to the study treatment and the ocular injection procedure. If the event is due to lack of efficacy or progression of underlying illness (i.e. progression of the study indication) the assessment of causality to study treatment will usually be 'Not suspected'. The rationale for this guidance is that the symptoms of a lack of efficacy or progression of underlying illness are not caused by the trial drug, they happen in spite of its administration and/or both lack of efficacy and progression of underlying disease can only be evaluated meaningfully by an analysis of treatment arms, not on a single patient.
3. Its duration (start and end dates) or if the event is ongoing, an outcome of not recovered/not resolved must be reported.

4. Whether it constitutes a SAE (see for definition of SAE) and which seriousness criteria have been met.
5. Action taken with the study treatment. All AEs must be treated appropriately. Treatment may include one or more of the following:
  - No action taken (e.g. Further observation only)

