  - Investigational treatment interrupted/withdrawn
  - Concomitant medication or non-drug therapy given
  - Patient hospitalized/patient's hospitalization prolonged (see [Section 10.1.2](#) for definition of SAE)
6. Its outcome:
  - Not recovered/not resolved
  - Recovered/resolved
  - Recovered/resolved with sequelae
  - Fatal or unknown.
7. Its location (ocular event / non ocular event)

Conditions that were already present at the time of informed consent should be recorded in the medical history of the patient.

Adverse events (including lab abnormalities that constitute AEs) should be described using a diagnosis whenever possible, rather than individual underlying signs and symptoms.

Adverse event monitoring should be continued until 30 days (safety follow-up) after the last administration of study treatment (see “Post-treatment follow-up period” in [Section 3](#)).

Once an AE is detected, it must be followed until its resolution or until it is judged to be permanent (e.g. continuing at the end of the study), and assessment must be made at each visit (or more frequently, if necessary) of any changes in severity, the suspected relationship to the interventions required to treat it, and the outcome.

Information about adverse drug reactions for the investigational drug can be found in the IB.

Abnormal test results constitute AEs only if they fulfill at least one of the following criteria:

- they induce clinical signs or symptoms
- they are considered clinically significant
- they require therapy

Clinically significant abnormal test results must be identified through a review of values outside of normal ranges/clinically notable ranges, significant changes from Baseline or the previous visit, or values which are considered to be non-typical in patients with the underlying disease. Investigators have the responsibility for managing the safety of individual patients and identifying AEs.

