The by-patients listing will include: SOC/PT/Verbatim term, start date, end date, severity, relationship to study treatment and procedures, whether or not it is a SAE, action taken with study treatment and outcome. Duration will be calculated as (end date – start date + 1) and for ongoing AE (last visit date – start date + 1) by ocular and non-ocular. For ocular then it will be presented by any eye, study eye and fellow eye.

A summary of action taken with number and percentage of patients will presented with dose increased, no dose change, dose reduced, treatment interrupted, drug withdrawn, not applicable and unknown.

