2.9.1.1 Adverse events of special interest / grouping of AEs

The number (%) of patients with AESIs will be summarized by standardized MedDRA query and PT. Listing will also be provided.

Case Retrieval Sheet (CRS) with the exact composition of the AE groupings is to be used to map reported AEs to the AESI groupings. This file may be updated (i.e.live document) based on review of accumulating trial data, and therefore the groupings are also subject to potential change. The most up-to-date version of the CRS will be used at the time of the analysis.

The number and percentage of patients having any AESI, AESI by SOC (confirmed by SRC) and PT will be presented.

The number and percentage of patients for AESI type along with incidence rate per patient and per 1000 injection will be provided. Incidence rate per patient is defined as number of patients in AESI type/total number of patients in safety analysis set and incidence rate per 1000 injection is define as (number of occurrence of AESI type/total number of injections)*1000.

The number and type of AESI will be plotted according to the time after last brolucizumab injection and time since first brolucizumab injection.

Summary statistics for change from baseline in BCVA after end date of AESI will be provided for each AESI type and change from baseline in BCVA will be plotted overall and for each type of AESI.

Patients demographics, baseline characteristics and medical history will be provided for AESI patient with safety set.

2.9.2 **Deaths**

A separate summary of deaths including on-treatment and post-treatment deaths will be provided.

All deaths in the clinical database will be listed with the investigator-reported principal cause. Deaths occurring after the first dose of study treatment until 30 days after the date of last treatment will be summarized. In addition, deaths occurring after the first dose of study treatment until the date of last treatment will also be summarized.

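### The only AESI-specific vision statistics are anchored to the AESI end date, so events that never close have no time point in them

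*SAP*

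**What the plan says.** SAP Addendum 2.9.1.1 plans, for AESIs: "Summary statistics for change from baseline in BCVA after end date of AESI will be provided for each AESI type". The same sentence adds that "change from baseline in BCVA will be plotted overall and for each type of AESI", and the section also plans an AESI listing. The plot carries no stated end-date limit. The text does not say which visit after the end date is used.

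Protocol 10.1.1 asks for start and end dates, but "if the event is ongoing, an outcome of not recovered/not resolved must be reported". Once detected, an event is handled as follows: "it must be followed until its resolution or until it is judged to be permanent (e.g. continuing at the end of the study". An event can therefore stay open through the whole study.

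The SAP foresees open events in one place. For AE duration in the by-patient listing (2.9.1) it has a substitute "for ongoing AE (last visit date – start date + 1". Section 5.1.2 imputes AE start dates only, and Section 2.9 rules out imputation of missing safety data.

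Protocol 6.1.4, 8.4.3 and 9.1.1 stop study treatment after intraocular inflammation (IOI), retinal vasculitis or retinal vascular occlusion. Protocol 9.1.1 and Table 8-1 keep BCVA collection going to Week 48 after that.

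**The concern.** To enter the table, a patient needs an AESI end date and a BCVA after it. Whether an event has an end date depends on how it turned out, so entry is selected on outcome. Eyes with persistent inflammation, vasculitis or occlusion are the ones without a qualifying date.

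This touches the drug's main safety question. Protocol 4.5 says these events can cause severe vision loss. They were the main reason for Amendment 3, the safety reason for Amendment 2, and part of Amendment 4, whose main reason was sample size. A reader would take the table as the trial's numerical answer on vision after an AESI, when it would answer only for events that closed.

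**Working it through.** **Patient base, reproduced first.** Protocol 12.8.1 uses SD 35, a two-sided 95% interval and a half-width of 5.0. (1.96 × 35 / 5)² = 188.2, so 189; with Student's t the half-width at 189 is 5.02, which rounds to 5.0. 189 / 0.90 = 210. Both planned figures reproduce. The documents give no figure for the AESI vision table.

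**Does any rule supply an end date?**
- Protocol 10.1.1: an open event carries an outcome code in place of an end date.
- SAP 5.1.2: covers start dates only.
- SAP 2.9: no imputation in safety analyses.
- SAP 2.9.1: the last-visit substitute is for duration only.

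None applies to BCVA in 2.9.1.1.

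**How many patients?** Protocol 4.5 gives IOI-related rates of r = 3.2% (males) and 5.3% (females) in the two earlier phase 3 studies. It also says "Over 90% of IOI AEs were mild to moderate in severity and 79% resolved with no sequelae", which leaves 21%. That 21% mixes unresolved events with events resolved with sequelae, so it is a ceiling on the unresolved share u. It counts events, and is applied here to patients. The values 5% and 10% are assumptions.

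| r | u | AESI patients, 210r | No end date, 210ru | Chance of at least one, 1 − (1 − ru)^210 |
|---|---|---|---|---|
| 3.2% | 5% | 6.7 | 0.34 | 29% |
| 3.2% | 10% | 6.7 | 0.67 | 49% |
| 3.2% | 21% | 6.7 | 1.41 | 76% |
| 5.3% | 5% | 11.1 | 0.56 | 43% |
| 5.3% | 10% | 11.1 | 1.11 | 67% |
| 5.3% | 21% | 11.1 | 2.34 | 90% |

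**How far does the mean move?** Mean over all AESI patients = mean over resolved − u × gap, where gap is the extra loss in unresolved eyes. The documents give no gap; 5, 15 and 30 letters are assumed.

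| u | gap 5 | gap 15 | gap 30 |
|---|---|---|---|
| 5% | 0.25 | 0.75 | 1.5 |
| 10% | 0.5 | 1.5 | 3.0 |
| 21% | 1.05 | 3.15 | 6.3 |

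If the gap is zero, the shift is zero.

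**Illustration (assumed values).** Take ten AESI patients, eight resolved at −2 letters and two unresolved at −30. The end-date rule reports −2.0. All ten give (8 × −2 + 2 × −30) / 10 = −7.6. The share losing at least 15 letters goes from 0% to 20%.

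**The case against.** The SAP does not say that unresolved AESIs are omitted. It leaves programming detail to table shells and dataset specifications that are not part of these documents, and those could supply a date. Unresolved cases also remain visible in the AESI listing, in the AE listing with outcome, and probably in the BCVA plot. With about ten patients, individual displays carry much of the information. The secondary safety endpoint, AE incidence, is untouched.

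Most of this stands, and it limits the point to one descriptive table. It does not remove it: the written rule, followed as written, gives open events no time point, and neither the listing nor the plot yields a summary figure. The general BCVA loss categories in SAP 2.6.1.4 are not split by AESI. Protocol 12.4.3 censors efficacy data when treatment stops, and Protocol 12.5.1 carries the primary method to continuous secondary outcomes, so that table may not recover these eyes either.

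Three stronger readings are tempting and are not supported:
- A reader might infer that lasting vision loss in general is removed. Resolved with sequelae is a separate outcome in Protocol 10.1.1. Such events have an end date, and their loss stays in.
- A reader might infer that 21% were unresolved. That figure is only a ceiling.
- A reader might infer that one or two omitted eyes reverse the sign. With assumed values of +5 letters resolved and −30 unresolved in nine patients, two omitted eyes do: (7 × 5 − 2 × 30) / 9 = −2.8. One does not: (8 × 5 − 30) / 9 = +1.1. Neither letter value comes from the documents.

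**Conclusion.** The point holds for AESIs that are ongoing or not recovered, and for events ending after the last BCVA. Their absence from the AESI vision statistics follows from the SAP's wording, subject to any rule in specifications not seen here. Understatement of vision loss is the expected direction, on the assumption that unresolved eyes see worse.

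The size is small in patients and uncertain in letters: roughly 0 to 2 of 7 to 11 AESI patients, and 0.25 to 6.3 letters over the assumed ranges. The expected count also assumes that the earlier rates carry over. Those studies ran up to 96 weeks against 48 here, and the protocol does not state the period behind the rates, so 7 to 11 may be high.

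**What to change.** In SAP 2.9.1.1, for every patient with a study-eye AESI, resolved or not:
- summarise change from Baseline in BCVA at the last available measurement after AESI onset, up to Week 48;
- count patients losing at least 15 and at least 30 letters, thresholds already used in SAP 2.6.1.4;
- show results by outcome: resolved, resolved with sequelae, not recovered or ongoing;
- report how many have no end date, and how many have no BCVA after onset.

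The after-end-date summary can stay as a supplement for resolved events. Worst BCVA after onset is optional: it is the minimum of repeated noisy values and also picks up decline from the underlying disease. The last available value is likewise not a pure AESI effect, which a footnote can say.

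A separate, minor wording conflict should be reconciled. Protocol 9.1.1 lists BCVA among items for which "the following data should be collected at clinic visits or via telephone/email contact", while Table 8-1 specifies an ETDRS score and Protocol 8.3.3 describes chart testing. The end-date point does not depend on it.

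The cost is SAP wording, one reprogrammed table from BCVA already due for collection, and one protocol clarification. The reported figure may look less favourable.

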2.9.3 Laboratory data

Not applicable

2.9.4 Other safety data

Not applicable

2.9.4.1 ECG and cardiac imaging data

Not applicable

2.9.4.2 Vital signs

Vital signs will include blood pressure and pulse rate measurements.

All vital signs data will be listed by patient, and visit, and if ranges are available, abnormalities will be flagged. Abnormal values are marked in Section 5.3. All data, including data from unscheduled visits, will be considered when identifying abnormal values. Analysis of vital sign measurements using summary statistics for the change from Baseline for each post-Baseline

visit will be performed. These descriptive summaries will be presented for each vital sign. Change from Baseline will only be summarized for patients with both Baseline and post-Baseline values.

2.10 Pharmacokinetic endpoints

Not applicable

2.11 PD and PK/PD analyses

Not applicable

2.12 Biomarkers

Not applicable.

2.13 Other exploratory analyses

Not applicable.

2.14 Interim analysis

The analysis based on the Week 12 data, i.e. data up to and including Week 12 will be the primary (first) analysis for this study.

A second planned analysis of the data after the EOS/Week 48 visit will be performed once all patients have completed or prematurely discontinued the study.

3 Sample size calculation

The primary objective of the study is to evaluate the effect of brolucizumab on CNV lesion area as measured by OCT-A in nAMD patients starting treatment with brolucizumab. This will be evaluated by the percentage change in CNV lesion area measured by OCT-A from Baseline to Week 12. The sample size calculation is based on the hypothesis of a standard deviation of 35% for this reduction proportion (Miere et al 2018).

A sample size of 180 to 400 patients produces a 2-sided 95% CI with a distance from the mean to the limits ranges from 5.1 to 3.4 when the estimated standard deviation is 35.0 (nQuery Advisor version 7.0). Therefore, to have a precision of 5%, a sample size of 189 patients will be needed (Table 3-1).

To take into account a dropout rate and uninterpretable images of 10%, a total of 210 patients will be included.

Table 3-1 Confidence intervals for one mean numeric results for 2-sided confidence intervals with unknown standard deviation

Confidence Level	Sample Size (N)	Distance from Mean to Limits	Standard Deviation (S)
0.950	180	5.1	35.0
0.950	189	5.0	35.0

For business use only	Page 31 of 39	
	CRTH258AFR01	

Novartis		
SAP Addendum	Version	1.0

0.950	233	4.5	35.0
0.950	250	4.4	35.0
0.950	300	4.0	35.0
0.950	350	3.7	35.0
0.950	385	3.5	35.0
0.950	400	3.4	35.0

4 Change to protocol specified analyses

5 Appendix

5.1 Imputation rules

5.1.1 Study treatment

The following rules should be used for the imputation of the dose end date for a given study treatment component:

Scenario 1

If the date of last IVT is completely missing and there is no end of treatment (EOT) page and no death date, the patient is considered as on-going.

The patient should be treated as on-going and the cut-off date should be used as the last dosing date.

Scenario 2

If the dose end date is completely or partially missing and the EOT page is available:

- Case 1: The dose end date is completely missing and the EOT completion date is complete, then this latter date should be used.
- Case 2: Only year (YYYY) of the dose end date is available and YYYY < the year of EOT date, then use 31DECYYYY.
- Case 3: Only year (YYYY) of the dose end date is available and YYYY = the year of EOT date, then use EOT date.
- Case 4: Both year (YYYY) and month (MMM) are available for dose end date and YYYY
 the year of EOT date and MMM < the month of EOT date, then use last day of the Month (MMM)

All other cases should be considered as a data issue and the statistician should contact the data manager of the study.

After imputation, compare the imputed date with start date of treatment.

If the imputed date is < start date of treatment, then use the treatment start date.

Otherwise, use the imputed date

Patients with missing start dates are to be considered missing for all study treatment component related calculations and no imputation will be made. If start date is missing then end-date should not be imputed.

5.1.2 AE date imputation

AE date imputation is based only on a comparison of the partial AE start date to the treatment start date as mentioned in the below.

- If the AE start date year value is missing, the date uncertainty is too high to impute a rational date. Therefore, if the AE year value is missing, the imputed AE start date is set to NULL.
- If the AE start date year value is less than the treatment start date year value, the AE started before treatment. Therefore:
 - 1. If the AE year is less than the treatment year and the AE month is missing, the imputed AE start date is set to the mid-year point (01JulYYYY).
 - 2. Else if the AE year is less than the treatment year and the AE month is not missing, the imputed AE start date is set to the mid-month point (15MONYYYY).
- If the AE start date year value is greater than the treatment start date year value, the AE started after treatment. Therefore:
 - 1. If the AE year is greater than the treatment year and the AE month is missing, the imputed AE start date is set to the year start point (01JanYYYY).
 - 2. Else if the AE year is greater than the treatment year and the AE month is not missing, the imputed AE start date is set to the month start point (01MONYYYY).
- If the AE start date year value is equal to the treatment start date year value:
 - 1. And the AE month is missing or the AE month is equal to the treatment start month, the imputed AE start date is set to one day after treatment start.
 - 2. Else if the AE month is less than the treatment start month, the imputed AE start date is set to the mid-month point (15MONYYYY).
 - 3. Else if the AE month is greater than the treatment start month, the imputed AE start date is set to the start month point (01MONYYYY).

	MON	MON < CFM	MON – CEM	MONS CEM	
	MISSING	MON > Crivi	MON = CFM	MON > CFM	
YYYY MISSING	NULL	NULL	NULL	NULL	
	Uncertain	Uncertain	Uncertain	Uncertain	
YYYY < CFY	(D) = 01JULYYYY	(C)= 15MONYYYY	(C)= 15MONYYYY	(C)= 15MONYYYY	
	Before Treatment Start	Before Treatment Start	Before Treatment Start	Before Treatment Start	
YYYY = CFY	(B)= TRTSTD+1	(C)= 15MONYYYY	(A)= TRTSTD+1	(A)= 01MONYYYY	
	Uncertain	Before Treatment Start	Uncertain	After Treatment Start	

YYYY > CFY	(E)= 01JANYYYY	(A)= 01MONYYYY	(A)= 01MONYYYY	(A)= 01MONYYYY	
	After Treatment Start	After Treatment Start	After Treatment Start	After Treatment Start	
Before Treatment Start		Partial indicates date prior to Treatment Start Date			
After Treatr	nent Start	Partial indicates date after Treatment Start Date			
Uncertain		Partial insufficient to determine relationship to Treatment Start Date			
LEGEND:					
(A)		MAX (01MONYYYY,TRTSTD+1)			
(B)		TRTSTD+1			
(C)		15MONYYYY			
(D)		01JULYYYY			
(E)		01JANYYYY			

